9.4.5. Survival Status

Category	Variable	Timepoint
Survival status	
Date of death (DD MMM YYYY)
 
Primary cause of death:
 
 • Complications related to invasive aspergillosis or mucormycosis; • Other disease complications; • SAE related to isavuconazole treatment; • SAE unrelated to isavuconazole treatment; • Other (specify); • Unknown. 	Post-index period

SAE = serious adverse event.

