9.9.1. Missing Data

It is anticipated that the degree of completeness for the study variables may vary due to unknown or undocumented data in the medical records. The number of patients with missing data for each variable will be summarized and reported. With the exception of the imputation of partial missing date values, no other imputation of missing values is anticipated; however, the impact of missing data on interpretation of findings will be acknowledged and discussed in the final study report. The SAP will further provide a detailed description of methods to deal with missing data and censoring.

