9.9.2. Planned Analysis

9.9.2.1. Analysis Plan for Primary Objectives

Mortality/survival rates will be summarized and reported. Clinical, radiological, and mycological response documented in the medical record will be summarized using proportions and counts for each category. Details of radiological and mycological assessments will be reported in a descriptive manner, including the type of assessment and the assessment findings. Definitions of response will be provided in the SAP. Time to response and all-cause mortality will be analyzed using the KM method and quartiles and 95% CIs will be reported.

Descriptive statistics will be used to describe all AEs and SAEs reported during the medical record review. The safety data described will include event type, relationship to isavuconazole treatment (where known), event severity, event seriousness, action taken with isavuconazole treatment and outcome of the event. Definitions of AEs and SAEs will be described in the SAP. Time from index treatment to first AE onset will be summarized.

Key timepoints of interest for assessment of treatment effectiveness, safety and survival outcomes will be at 6 weeks, 12 weeks, and 24 weeks after initiation of index treatment. In the cases that usual care visits do not directly coincide with these timepoints, the time windows for assessment of outcomes will be defined in the SAP.

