## 6 STATISTICAL METHODS AND ANALYSIS

### 6.1 STATISTICAL CONVENTIONS

Categorical variables will be reported as counts and frequencies of nonmissing observations. Continuous variables will be reported using the number of nonmissing observations, mean, standard deviation, median, first quartile, third quartile, minimum value, and maximum value. Time-to-event outcomes will be assessed using the Kaplan-Meier (KM) method and will be reported as descriptive statistics with 95% CIs. Results will be presented for the overall group (both disease types) and separately for invasive aspergillosis and mucormycosis. Additionally, subgroup analyses may be performed. If so, log-rank tests will be reported, and Cox regression will be employed with presentation of hazard ratios (HRs) and 95% CIs.

Unless otherwise specified, the time between two dates of interest (including time-to-event analyses) will be computed as the difference between the two calendar dates (e.g., date 2 – date 1) and expressed in days.

No imputation for missing values will be performed. Criteria for censoring in KM analyses will be described for each time-to-event outcome analyzed.

Example tables and figure descriptions for analyses described in this section (analysis tables and analysis figures) are provided in Appendix 1.

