### 6.3 ANALYSIS OF CLINICAL OUTCOMES

Each clinical outcome will be analyzed using counts and frequencies at weeks 6, 12, and 24, along with other descriptive information about the clinical outcome itself.

Additionally, time-to-event analyses anchored on the index date of isavuconazole initiation will be performed using the KM method. For each clinical outcome, the time-to-event analyses will result in a KM plot with summary statistics, including survival-time quartiles and KM estimates at weeks 6, 12, and 24 with accompanying 95% CIs. All analyses will be performed for invasive aspergillosis patients, mucormycosis patients, and for the total study population. If subgroup analyses are pursued, Cox regression will be employed to derive HRs and accompanying 95% CIs.

For the death outcome, patients will be categorized as dead, alive, or unknown at each timepoint of interest, and primary cause of death will be tabulated (Appendix 1, Analysis Table 5.1). For KM analyses, a documented death will comprise the event, and patients will be censored at the date when they are last known to be alive (Appendix 1, Analysis Figure 1; Appendix 1, Analysis Table 5.2).

For the clinical response outcome, patients will be categorized as having clinical success, having clinical failure, or unknown response at each timepoint of interest will be tabulated (Appendix 1, Analysis Table 6.1). In addition, rates of reactivation of the same infection and rates of new infection will be documented overall and specific to whether these events occurred during isavuconazole treatment. For KM analyses, clinical response will comprise the event, and patients will be censored at the earliest timepoint of any of the following: loss to follow-up, end of study, or death (Appendix 1, Analysis Figure 2; Appendix 1, Analysis Table 6.2).

For radiological response, patients will be categorized as having a success, not having a response, unknown response, or not applicable (for the first assessment) at the relevant timepoints of interest (Appendix 1, Analysis Table 7.1). Additionally, radiological examination type and bodily location of the examination will be tabulated. For KM analyses, radiological response will comprise the event, and patients will be censored at the earliest timepoint of any of the following: loss to follow-up, end of study, or death (Appendix 1, Analysis Figure 3; Appendix 1, Analysis Table 7.2).

PFIZER CONFIDENTIAL

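### SAP 6.1 excludes all imputation although the protocol provides for imputing partial dates, which leaves documented events with an incomplete date without a computable Kaplan-Meier time

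*SAP*

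**What the plan says.** Protocol 9.9.1 states: "With the exception of the imputation of partial missing date values, no other imputation of missing values is anticipated". It then hands the detail over: "The SAP will further provide a detailed description of methods to deal with missing data and censoring".

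SAP 6.1 states, with no exception: "No imputation for missing values will be performed". The same section says that the time between two dates "will be computed as the difference between the two calendar dates", in days, unless otherwise specified. No rule for partial dates appears in SAP 6.1 to 6.6.

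For mortality, SAP 6.3 says that "a documented death will comprise the event, and patients will be censored at the date when they are last known to be alive". For clinical response, "clinical response will comprise the event, and patients will be censored at the earliest timepoint of any of the following". Three censoring reasons are then listed: death, the study ending, and the patient being lost. Radiological and mycological response (SAP 6.3) and time to first adverse event (SAP 6.4) are built in the same way.

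These analyses serve the primary objectives. Protocol 9.9.2.1 says: "Time to response and all-cause mortality will be analyzed using the KM method and quartiles and 95% CIs will be reported".

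Protocol 9.4.5 collects the date of death in day-month-year form and gives no convention for an unknown part. Protocol 9.10 says that the system turns the entered dates into durations and that the dates themselves are not kept.

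**The concern.** The two documents give opposite instructions on partial dates, and the one that was meant to supply the method supplies none. A chart may say that a patient died in a given month without giving the day. Under SAP 6.3 that patient has had the event. Under SAP 6.1 the event has no time, because one of the two dates in the subtraction is incomplete and may not be completed.

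Whoever programs the analysis must then choose: leave the patient out, censor at the last date known alive, or impute against the SAP. For mortality the first two choices both lower the estimate. If the choice is made once the data are in hand, it is also a post hoc decision about which deaths count. The same gap affects the three response outcomes and time to first adverse event.

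**Working it through.** **1. The texts side by side.**

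| Question | Protocol | SAP |
|---|---|---|
| Impute partial dates? | Yes, the sole exception (9.9.1) | No exception stated (6.1) |
| Who gives the method? | The SAP (9.9.1) | No method in 6.1–6.6 |
| How is an event time obtained? | System computes durations, dates not kept (9.10) | Subtraction of calendar dates (6.1) |
| What is the death event? | – | Any documented death (6.3) |

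A death recorded by month and year meets the event definition and fails the time computation. Nothing in the SAP resolves this.

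**2. Size: inputs.** The plan has no figure to reproduce here, so the following is an illustration.
- Day-42 mortality *p*: 19% in aspergillosis and 33% in mucormycosis (Protocol 9.5).
- Share *f* of deaths with a partial date: not given; assumed 2%, 5%, 10% and 20%.
- Constant hazard to day 168 (24 weeks): assumed. The proportion dead by day 168 is then D = 1 − (1 − p)^4, because 168/42 = 4. This gives 1 − 0.81^4 = 0.570 and 1 − 0.67^4 = 0.798.

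**3. Formulas for day-42 mortality.**
- Partial-date deaths dropped: p(1 − f) / (1 − fD). Later partial-date deaths leave the denominator too.
- Partial-date deaths censored at about the time of death: 1 − (1 − p)^(1 − f).

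For aspergillosis at f = 10%: dropped, 0.171 / (1 − 0.057) = 18.1%; censored, 1 − 0.81^0.9 = 17.3%. The shortfalls from 19% are 0.9 and 1.7 points.

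**4. Simulation.** Kaplan-Meier on 60,000 simulated patients with the same constant hazard. Partial-date deaths were dropped, censored 0–14 days before death, or imputed to mid-month.

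| | f | Full data | Dropped | Censored | Mid-month |
|---|---|---|---|---|---|
| Aspergillosis | 2% | 19.1 | 19.0 | 18.8 | 19.1 |
| | 5% | 19.1 | 18.7 | 18.3 | 19.1 |
| | 10% | 19.1 | 18.4 | 17.5 | 19.1 |
| | 20% | 19.1 | 17.3 | 15.8 | 19.2 |
| Mucormycosis | 2% | 33.1 | 32.9 | 32.5 | 33.0 |
| | 5% | 33.1 | 32.7 | 31.8 | 33.1 |
| | 10% | 33.1 | 32.3 | 30.5 | 33.1 |
| | 20% | 33.1 | 31.5 | 27.7 | 33.1 |

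The simulated shortfalls in aspergillosis (dropped to censored) are 0.1–0.3 points at 2%, 0.4–0.8 at 5%, 0.7–1.6 at 10% and 1.8–3.3 at 20%. The formulas give 0.2–0.3, 0.4–0.9, 0.9–1.7 and 1.8–3.5. The two agree within about 0.2 points; sampling error and the assumed gap before death account for the rest. In mucormycosis at 20%, censoring costs 33.1 − 27.7 = 5.4 points. Mid-month imputation stays within about 0.1 point of the full-data value throughout.

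**5. Scale.** With the full target of 600 patients at 19%, the 95% half-width is 1.96 × √(0.19 × 0.81 / 600) = 3.1 points. The shortfall at f = 10% lies within that margin, but it goes in one direction only and does not shrink with sample size.

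**The case against.** A reader might infer that the SAP drops or censors known deaths. It says neither. SAP 6.3 makes a documented death the event, so censoring one would break the SAP's own definition, and exclusion is not mentioned. The SAP is silent on undated events; the downward bias follows only if a programmer takes one of those two routes.

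A reader might also infer that partial death dates will be common, for instance after discharge. The documents do not show this. Protocol 9.11 lists items that are less likely to be fully documented, and date of death is not among them. The data system has completeness checks and queries followed to resolution (Protocol 9.6.1, 9.7 and 9.8). The warnings about care outside the site's records point at least as much to unknown vital status as to a known death without a day. The protocol's exception shows that partial dates were foreseen, not that they are frequent.

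Larger figures for exclusion are tempting: 0.19(1 − f)/(1 − 0.19f) gives 18.2%, 17.4% and 15.8% at 5%, 10% and 20%. That formula removes only the partial-date deaths up to day 42. Follow-up runs well beyond that, and later partial-date deaths would leave the denominator as well, so the expected loss from dropping is smaller.

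Two further points have some force. Protocol 9.9 lets the SAP modify the plan, and missing values could be read as wholly absent values. But the SAP does not present its sentence as a change and gives no reason, and Protocol 9.9.1 itself treats partial dates as a kind of missing value. Finally, the Appendix 1 table shells are in an embedded file that was not available, so a footnote on dates cannot be excluded; the SAP text refers to none.

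**Conclusion.** The point holds as a conflict between a stated SAP rule and the protocol, with a consequence for the primary analyses. Followed literally, SAP 6.1 leaves any documented death, response or first adverse event with an incomplete date without an event time. It affects only those records. Some week 6, 12 and 24 statuses can still be settled when the recorded month alone decides them.

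The size is conditional on the unknown share of partial dates, on those deaths being dropped or censored, and on a constant hazard. It is negligible at 2% and worth preventing at 10% or more, above all in the small mucormycosis group. No size was worked out for responses or adverse events. Confidence is high for the contradiction and low for how much bias would arise in practice. The change should be made because it is cheap and settles the handling in advance.

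**What to change.** Replace the SAP 6.1 sentence with wording such as: *No imputation will be done except of partial dates.* Then pre-specify the rule:

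- A missing day is set to mid-month. The result stays within the recorded month, is bounded below by the index date and (for deaths) the last date known alive, and is bounded above by the end of follow-up.
- State what is done when the month is also missing.
- Report the number of imputed dates for each outcome.
- Repeat the Kaplan-Meier analyses with the earliest and the latest possible dates.
- In Analysis Table 5.1, count a patient known to have died by a timepoint as dead, whatever the precision of the date.

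Reconcile Protocol 9.10 with SAP 6.1 at the same time. If dates are absent from the data set, neither the subtraction nor any imputation can be done at analysis. Either keep the dates (or the known parts of partial dates) for analysis, or apply the rule inside the data-capture system when it derives durations.

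If the sponsor does intend no imputation at all, the exception should come out of Protocol 9.9.1 and the SAP should say how events with incomplete dates are handled.

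The cost is a few sentences, a short date derivation and one sensitivity run. The Protocol 9.10 point may add a change to the data-capture set-up, depending on which route is chosen.

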### 6.2 CHARACTERIZATION OF STUDY POPULATION

Descriptive statistics will be used to summarize demographics and medical history assessed at the closest date available to the index date of the study population (Appendix 1, Analysis Table 1) and comorbid medical conditions assessed within 30 days prior to the index date (Appendix 1, Analysis Table 2). Because only year of birth was solicited on the data collection form, the calculation of exact age will not be precise and will be estimated as the year of the date of interest (e.g., data collection, death, last known follow-up visit) minus the year of birth. Height is collected in either feet and inches or centimeters; weight is collected as stone and pounds or kilograms. Weight and height will be summarized using kilograms and centimeters, respectively, for all analyses. Thus, height collected as feet and inches will be converted to centimeters  $[(12 \times \text{feet} + \text{inches}) \times 2.54]$ , and weight collected as stone and pounds will be converted to kilograms  $[(14 \times \text{stone} + \text{pounds}) \div 2.205]$ . To calculate body mass index, height in centimeters will first be converted to meters (centimeters  $\div 100$ ), then the weight in kilograms will be divided by the square of the height in meters to yield a measurement with the units of kilograms per square meters.

Fungal disease characteristics (e.g., disease type, days from suspected diagnosis to initiation of isavuconazole, method of infection confirmation, localization) for the study population will be summarized from the closest assessment to the index date within the

PFIZER CONFIDENTIAL

CT24-WI-GL03-RF03 1.0 *Non-Interventional Statistical Analysis Plan For Secondary Data Collection*  
Study 16-Sep-2020  
Page 14 of 19

pre-index period; however, if no pre-index period assessments are available, the closest assessment in the post-index period will be used (Appendix 1, Analysis Table 3). Antifungal drug use assessed within 1 year prior to index treatment and prior treatment history assessed within 30 days prior to the index date also will be summarized (Appendix 1, Analysis Table 4). Characteristics to be assessed include antifungal type, treatment switch to isavuconazole for the same infection, reason for switch to the index treatment, and other prior treatment history (including antibiotics, surgery, corticosteroids, and immunosuppressants).

### 6.3 ANALYSIS OF CLINICAL OUTCOMES

Each clinical outcome will be analyzed using counts and frequencies at weeks 6, 12, and 24, along with other descriptive information about the clinical outcome itself.

Additionally, time-to-event analyses anchored on the index date of isavuconazole initiation will be performed using the KM method. For each clinical outcome, the time-to-event analyses will result in a KM plot with summary statistics, including survival-time quartiles and KM estimates at weeks 6, 12, and 24 with accompanying 95% CIs. All analyses will be performed for invasive aspergillosis patients, mucormycosis patients, and for the total study population. If subgroup analyses are pursued, Cox regression will be employed to derive HRs and accompanying 95% CIs.

For the death outcome, patients will be categorized as dead, alive, or unknown at each timepoint of interest, and primary cause of death will be tabulated (Appendix 1, Analysis Table 5.1). For KM analyses, a documented death will comprise the event, and patients will be censored at the date when they are last known to be alive (Appendix 1, Analysis Figure 1; Appendix 1, Analysis Table 5.2).

For the clinical response outcome, patients will be categorized as having clinical success, having clinical failure, or unknown response at each timepoint of interest will be tabulated (Appendix 1, Analysis Table 6.1). In addition, rates of reactivation of the same infection and rates of new infection will be documented overall and specific to whether these events occurred during isavuconazole treatment. For KM analyses, clinical response will comprise the event, and patients will be censored at the earliest timepoint of any of the following: loss to follow-up, end of study, or death (Appendix 1, Analysis Figure 2; Appendix 1, Analysis Table 6.2).

For radiological response, patients will be categorized as having a success, not having a response, unknown response, or not applicable (for the first assessment) at the relevant timepoints of interest (Appendix 1, Analysis Table 7.1). Additionally, radiological examination type and bodily location of the examination will be tabulated. For KM analyses, radiological response will comprise the event, and patients will be censored at the earliest timepoint of any of the following: loss to follow-up, end of study, or death (Appendix 1, Analysis Figure 3; Appendix 1, Analysis Table 7.2).

PFIZER CONFIDENTIAL

CT24-WI-GL03-RF03 1.0 *Non-Interventional Statistical Analysis Plan For Secondary Data Collection*  
Study 16-Sep-2020  
Page 15 of 19

For the mycological response outcome, patients will be categorized having the infection eradicated, presumed eradicated, not eradicated (failure), unknown response, or not applicable (for the initial assessment) at relevant timepoints of interest. Additionally, mycological examination type and biomarker categories will be tabulated at post-baseline visits (Appendix 1, Analysis Table 8.1). For KM analyses, mycological response (eradication or presumed eradication) will comprise the event, and patients will be censored at the earliest timepoint of any of the following: loss to follow-up, end of study, or death (Appendix 1, Analysis Figure 4; Appendix 1, Analysis Table 8.2)

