9.3.1.2. Eligibility Period

The eligibility period, wherein potentially eligible patients are identified for enrollment, will be from October 15, 2015 (date of isavuconazole approval by the EMA in the EU), to June 30, 2019.^l The end date of the eligibility period ensures that the latest date of isavuconazole initiation will occur at least 6 months before the end of December 2019 (after which point the medical records may contain data related to the COVID-19 pandemic, which is not of interest for this study). This will allow a minimum of 6 months of follow-up from the date of isavuconazole initiation unless the patient dies or is lost to follow-up within this timeframe (see [Figure 1](#)).

^k Dates of medical record abstraction are subject to change based on the volume of potentially eligible patients during the timeframe of the current eligibility period, the timing of study start-up, and the effect of the COVID-19 pandemic on the availability of members of ethical review boards, institutional review boards, and availability of site staff.

^l The eligibility period end date is subject to change based on the timing of medical record abstraction and the anticipated number of potentially eligible patients during the proposed eligibility timeframe.

Figure 1. Overview of Study Periods and Examples of Eligible Cases

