9.3.1.3. Data Collection (Chart Abstraction) Periods

Patients who initiate isavuconazole treatment (index event) during the eligibility period (October 15, 2015, to June 30, 2019)^m will be identified and screened for inclusion/exclusion criteria for enrollment into the study.

[figure not shown]
The two main study periods for data collection from each patient's medical chart are:

- **Pre-index event period:** Baseline data on demographics and medical history will be collected based on all available information in medical records before the index event.

^m The eligibility period end date is subject to change based on timing of medical record abstraction and anticipated number of potentially eligible patients during the proposed eligibility timeframe.

- **Post-index event period:** The timeframe for follow-up data collection will begin one day post-index treatment initiation and end at the earliest of the following: 6 months after post-index treatment discontinuation, death, or loss to follow-up, or December 31, 2019 (see [Figure 1](#) and [Figure 2](#)). Key timepoints of interest for assessment of clinical response and safety will be at 6 weeks, 12 weeks, and 24 weeks after initiation of index treatment (see [Figure 2](#)).

Figure 2. Data Collection Periods and Timepoints for Each Patient

FU = follow up.

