TDM	
Was TDM conducted?
 
 • Yes; • No; • Unknown. 
Date of TDM (DD MMM YYYY)
 
Outcome of TDM:
 
 • Treatment modification; • Treatment discontinuation; • None; • Other (specify); 	Post-index period

Category	Variable	Timepoint
Discontinuation of index treatment	
 Unknown. 
Discontinuation of index treatment:
 
 Yes; No; Unknown. 	Post-index period
	Date of discontinuation (DD MMM YYYY)	
	Reason for discontinuation:	
	
 Patient completed planned course of treatment; Lack of response to treatment; AE; Patient decision (unrelated to AEs); Treatment success (resolution of invasive fungal infection); Death (unrelated to therapy); TDM; Drug-drug interaction; Other (specify); Unknown. 	
Switch to a new antifungal drug after discontinuation of index treatment	
Switch to a new antifungal agent after discontinuation:
 
 Yes; No; Unknown. 	Post-index period
	Start date of subsequent antifungal agent (DD MMM YYYY)	
	End date of subsequent antifungal agent (DD MMM YYYY)	
	Type of new antifungal agent:	
	
 Liposomal amphotericin B; Voriconazole; Posaconazole; Caspofungin; Anidulafungin; Micafungin; Other (specify); Unknown. 	
Other subsequent antifungal use after end of index treatment	Type of new antifungal drug:	Post-index period
	
 Liposomal amphotericin B; Voriconazole; Posaconazole; 	

Category	Variable	Timepoint
	
 • Caspofungin; • Anidulafungin; • Other (specify); • Unknown. 	
	Start date of subsequent antifungal agent (DD MMM YYYY)	
	End date of subsequent antifungal agent (DD MMM YYYY)	
Index treatment administered as part of antifungal combination therapy	
Index treatment administered as part of antifungal combination therapy:
 
 • Yes; • No; • Unknown. 
Type of therapy administered in combination with isavuconazole:
 
 • Liposomal amphotericin B; • Voriconazole; • Posaconazole; • Caspofungin; • Anidulafungin; • Micafungin; • Other (specify); • Unknown. 	Index date, post-index period
	Start date of therapy administered in combination with isavuconazole (DD MMM YYYY)	
	End date of therapy administered in combination with isavuconazole (DD MMM YYYY)	

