9.9. Data Analysis

This study is primarily descriptive in nature. Categorical variables will be reported as counts (n) and frequencies (%). Continuous variables will be reported using mean, standard deviation, median, minimum and maximum, interquartile range, and range. Time to event outcomes will be assessed using the KM method and will be reported as descriptive statistics (eg, median time to event) with 95% CI. Results will be presented for the overall group (both disease types) and separately for invasive aspergillosis and mucormycosis.

The statistical analysis plan (SAP) will provide a detailed description of analytic populations, analyses to be performed, and methods to deal with missing data and censoring.

Depending on the overall sample size, subgroup analyses may be conducted for main study outcomes (eg, by country, by diagnosis).

Detailed methodology for summary and statistical analyses of data collected in this study will be documented in a SAP, which will be dated, filed, and maintained by the sponsor. The SAP may modify the plans outlined in the protocol; any major modifications of primary outcome definitions or their analyses would be reflected in a protocol amendment. The SAP will define all planned analytic populations and subpopulations, including definitions of overall response and AEs of interest. The SAP will further provide a detailed description of analyses to be performed.

Any known deviations from the planned analyses, the reason for such deviations and all alternative/additional statistical analyses that may be performed as well as the final statistical analysis must be described in a revised SAP before completion of data collection.

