**Figure 1 Overview of Study Periods and Examples of Eligible Cases**

### 4.2 STUDY PERIODS

[figure not shown]
The index event is defined as the first initiation of isavuconazole treatment for the invasive fungal infection. The index event serves as the point at which (1) a patient

PFIZER CONFIDENTIAL

qualifies for study inclusion, (2) patient follow-up begins, and (3) the patient becomes at risk for experiencing study outcomes. Study periods for data extraction and variable assessment are defined relative to the index event (Figure 1).

- **Eligibility period:** The index date must occur within the eligibility period, which is the timeframe wherein potentially eligible patients are identified for enrolment. *The dates comprising the eligibility period will be October 15, 2015 (date of isavuconazole approval by the EMA in the EU), to June 30, 2019. The end date of the eligibility period ensures that the latest date of isavuconazole initiation will occur at least 6 months before the end of December 2019 (after which point the medical records may contain data related to the COVID-19 pandemic, which is not of interest for this study). This definition will allow for a minimum of 6 months of follow-up from the date of isavuconazole initiation unless the patient dies or is lost to follow-up within this timeframe.*
- **Pre-index period:** *Baseline data on demographics and medical history will be collected based on all available information in medical records before the index event.*
- **Post-index period:** *The timeframe for follow-up data collection will begin one day post-index treatment initiation and end at the earliest of the following: 6 months after post-index treatment discontinuation, death, or loss to follow-up (Figure 1 and Figure 2). Key timepoints of interest for assessment of clinical response and safety will be at 6 weeks, 12 weeks, and 24 weeks after initiation of index treatment (Figure 2).*

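### Mortality estimates beyond about week 26 rest on a risk set selected by treatment length, so any late survival quartile may be informatively censored; stop the mortality curve at week 24

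*SAP*

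**What the plan says.** **End of observation.** Protocol 9.3.1.3 closes each patient's data window at the earliest of "6 months after post-index treatment discontinuation, death, or loss to follow-up, or December 31, 2019". SAP 4.2 has "6 months after post-index treatment discontinuation, death, or loss to follow-up", without the calendar date. Survival status is collected only in this post-index window (Protocol 9.4.5).

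**Minimum follow-up.** On the 30 June 2019 eligibility limit, Protocol 9.3.1.2 says: "This will allow a minimum of 6 months of follow-up from the date of isavuconazole initiation", barring death or loss to follow-up.

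**Reasons for stopping.** Protocol 9.4.2 lists "Lack of response to treatment", adverse events and treatment success. It also lists completed course, patient decision, drug monitoring, drug interaction, death, other and unknown.

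**Planned summaries.** Protocol 9.9.2.1: "Time to response and all-cause mortality will be analyzed using the KM method and quartiles and 95% CIs will be reported". Protocol 9.9 gives the median as an example: "reported as descriptive statistics (eg, median time to event) with 95% CI". SAP 6.3 asks for a Kaplan-Meier plot and summaries "including survival-time quartiles and KM estimates at weeks 6, 12, and 24 with accompanying 95% CIs", for each disease and overall. For death, patients are censored when last known alive. The protocol leaves censoring methods to the SAP. The SAP gives no truncation time, no rule for a late quartile and no sensitivity analysis.

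**The concern.** Kaplan-Meier treats a censored patient as having the same later risk as those still under observation. Here a patient who stops isavuconazole in the first week leaves observation at about 6 months, while one treated for several months is watched for correspondingly longer. Beyond about week 26, remaining in the risk set requires a longer course. If course length is related to prognosis, as several listed stop reasons suggest it could be, the later curve reflects patients with long courses but would be read as describing the whole cohort.

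All-cause mortality is a primary outcome, and its quartiles are a planned summary. What is at stake is any quartile, and any part of the plotted curve, that lies past that point.

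**Working it through.** **1. The plan's own figures.** From 30 June to 31 December 2019 is 184 days (184/7 = 26.3 weeks). A stop immediately after the index date plus 6 months gives about 182.6 days (26.1 weeks). Both exceed 168 days (week 24); 30 June 2019 + 168 days is 15 December 2019. The stated minimum follow-up is reproduced, and neither the stop-date rule nor the calendar cut-off can censor a patient before week 24.

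The 19% day-42 rate in Protocol Table 1 also reproduces its Wilson widths: 8.98, 9.96, 12.41 and 14.83 points for N = 292, 237, 152 and 106, against 9.0, 10.0, 12.5 and 15.0 stated.

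**2. Where the quartiles fall.** Inputs from Protocol 9.5 are day-42 mortality m = 19% (aspergillosis, SECURE) and 33% (mucormycosis, VITAL). The documents give no expected mortality for isavuconazole after day 42, so the curve shape is assumed: Weibull with shape k, where k = 1 is constant hazard and k < 1 is declining hazard. With H = −ln(1 − m), the time by which a fraction q has died is

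t = 6 weeks × [−ln(1 − q)/H]^(1/k).

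H = 0.2107 for aspergillosis and 0.4005 for mucormycosis. For example, the aspergillosis upper quartile at k = 1 is 6 × 1.3863/0.2107 = 39.5 weeks.

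| Quartile (week) | Asp. k = 1 | k = 0.8 | k = 0.5 | Muc. k = 1 | k = 0.8 | k = 0.5 |
|---|---|---|---|---|---|---|
| Lower | 8.2 | 8.9 | 11.2 | 4.3 | 4.0 | 3.1 |
| Median | 19.7 | 26.6 | 64.9 | 10.4 | 11.9 | 18.0 |
| Upper | 39.5 | 63.2 | 259.7 | 20.8 | 28.3 | 71.9 |

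- The aspergillosis median passes week 26 only if k is below about 0.81; the mucormycosis median only if k is below about 0.37.
- The aspergillosis upper quartile comes before week 26 only if the hazard rises (k above about 1.28).
- The lower quartile stays before week 26 for both diseases over the whole range examined (k = 0.3 to 1.2).

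**3. Size of the possible bias.** The documents give no distribution of treatment length, so this step is illustrative. Assumptions:

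- 400,000 patients, with index dates uniform over the eligibility period;
- lognormal treatment length with median 60 days and log-SD 0.8;
- lognormal frailty with SD 1 (this makes the cohort hazard decline further, so the medians are later than in step 2);
- mortality matched to the documents' day-42 rates;
- correlation ρ between treatment length and frailty of −0.6 (long courses healthier), 0 or +0.6 (long courses sicker);
- censoring at stop + 182.6 days or 31 December 2019, whichever is earlier.

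Results:

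- Weeks 6, 12, 24 and 26: Kaplan-Meier minus true survival is 0.0 points in every scenario.
- Week 52: +2.1 to +4.0 points at ρ = −0.6, about 0 at ρ = 0, and −4.2 to −6.8 at ρ = +0.6. Between 0 and 6% of the cohort is still at risk, down from 30–67% at week 26.
- Aspergillosis median at k = 0.7: true about 48 weeks; reported 65, 48 and 42 for ρ = −0.6, 0 and +0.6.
- Aspergillosis median at k = 0.5: true about 109 weeks; reported not reached, 103 and 65.
- Aspergillosis median at k = 1: true and reported both about 25.6 weeks.
- Mucormycosis median: weeks 12 to 24, no bias in any scenario.

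A separate simulation used three treatment-length groups (means 20, 45 and 200 days), a two- to three-fold difference in later hazard, and the SAP's stop rule without the calendar date. It put the median off by about 40 to 87 days and day-365 mortality off by about 4 to 6.5 points, again in either direction.

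**The case against.** A reader might infer that the planned median survival time is informatively censored as it stands. The documents do not support that. It needs a median beyond about week 26 and a link between treatment length and later mortality, and they supply neither. Under constant hazard both medians fall earlier. The mucormycosis median would be affected only with a very steep fall in hazard.

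Nor are all stop reasons tied to prognosis: drug interaction, drug monitoring and patient decision need not be. Success and lack of response point in opposite directions, so the net association could be small. Treatment length is also not the only selector: under the protocol the 31 December 2019 date ties late follow-up to calendar index date as well. And if charts hold last-alive dates beyond the window and these are used, censoring would differ; the SAP does not say.

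The study is descriptive, its key timepoints are weeks 6, 12 and 24, and late quartiles would carry wide intervals. In scenarios of the second kind with a true median of 381 days, 95% of estimated medians lay between about 250 and 510 days at N = 200, and between about 280 and 392 at N = 583. The first range supports the point that sampling error can swamp the bias. The second does not: it is centred near (280 + 392)/2 = 336 days, well below the truth, and a confidence interval does not correct that.

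Most of this stands and limits the point to late quartiles and the tail. It does not remove the point: under constant or declining hazard the aspergillosis upper quartile is either unreached or estimated in the affected region, and an untruncated plot shows that region wherever the median falls.

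**Conclusion.** The point holds in a limited form. Any survival quartile or part of the mortality curve beyond about week 26 is exposed to possibly informative censoring, because the risk set there is selected by treatment length. For aspergillosis this covers the upper quartile under constant or declining hazard, and the median only if the hazard declines (k below about 0.81). The direction is unknown. The size is roughly 2 to 7 points at week 52 under the assumed correlations, and nil if treatment length is unrelated to risk.

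The week 6, 12 and 24 estimates and the lower quartile are not affected, and the mucormycosis median probably is not. It may also be tempting to read the same bias into the response and first-AE curves. That has not been shown: only mortality was examined, and nothing in the documents places quartiles of those outcomes after week 26.

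This is a cheap improvement. It does not put the planned primary timepoint estimates in doubt.

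**What to change.** Add one sentence to SAP 6.3: the all-cause mortality Kaplan-Meier analysis is administratively censored at week 24 (day 168), and any quartile not reached by then is reported as 'not reached by week 24'. Limit the figure's time axis to match. Day 168 is the last planned timepoint; if the sponsor wants the remaining complete follow-up, the limit should be no later than about day 182. The same limit may be applied to the response curves and to the first-AE curve in SAP 6.4 for consistency.

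Separately, reconcile the end-of-follow-up definitions: the protocol includes 31 December 2019 and SAP 4.2 does not. The day-168 limit works under either.

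The cost is that the sparse late tail, and any median or upper quartile beyond week 24, are no longer reported, and that a day-168 limit gives up about two weeks of follow-up (182 − 168 = 14 days) that the stop rule leaves intact. No new data are needed and no planned timepoint estimate changes.
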